8.4.1.3 Time to first exacerbation

Time from randomisation to the first COPD exacerbation will also be used as a supportive variable to the primary objective, and is calculated as follows:

Start Date of first COPD exacerbation – Date of Randomisation + 1.

The time to first COPD exacerbation for subjects who do not experience an COPD exacerbation during the treatment period will be censored at the date of their last visit for the 56-week double-blind treatment period, or at the time point after which an exacerbation could not be assessed (for lost-to-follow-up subjects).

8.4.1.4 Forced expiratory volume in 1 second

The change from baseline to each of the post-randomisation visits (post Visit 4) up to and including the end of 56-week double-blind treatment visit (Visit 19) will be used as secondary efficacy variables. The pre-bronchodilator measurement recorded at Visit 4 will be used as baseline FEV₁. If the Visit 4 pre-bronchodilator measurement is missing, the last non-missing pre-bronchodilator value before Visit 4 will be used as baseline instead.

8.4.1.5 Annual rate of COPD exacerbations that are associated with an emergency room visit or a hospitalization

The annual rate of COPD exacerbations that are associated with an emergency room visit or a hospitalization will be a secondary efficacy variable.

In the statistical analysis, the number of COPD exacerbations that are associated with an emergency room visit or a hospitalization experienced by a subject during the 56-week double-blind treatment period will be used as response variable, and the logarithm of the subject's corresponding follow-up time will be used as an offset in the analysis to adjust for subjects having different exposure times during which the events occur.

Maximum follow-up time is approximately 56 weeks, and the follow-up time is derived as described in section [8.4.1.1](#).

8.4.1.6 Annual rate of healthcare encounters due to COPD

The annual rate of hospitalizations due to COPD, the annual rate of hospitalizations and emergency room visits combined due to COPD, the annual rate of unscheduled outpatient visits including unscheduled visits to study centres due to COPD and all unscheduled healthcare encounters combined due to COPD (hospitalizations, emergency room visits, unscheduled outpatient visits including unscheduled visits to study centres) will be secondary variables.

In the statistical analysis, the number of hospitalizations due to COPD, the number of emergency room visits and hospitalizations combined due to COPD, the number of unscheduled outpatient visits due to COPD and the number of all unscheduled healthcare encounters due to COPD experienced by a subject during the 56-week double-blind treatment period will be used as response variables in four different statistical models with the logarithm of the subject's corresponding follow-up time used as an offset in the analysis to adjust for subjects having different exposure times similar to COPD exacerbations as described in section 8.4.1.5. If multiple healthcare encounters are associated with one COPD exacerbation all the encounters will be counted for this endpoint.

8.4.2 Calculation or derivation of safety variable(s)

8.4.2.1 Safety variables

The following safety data will be collected: vital signs, physical examination, 12-lead ECG, haematology, clinical chemistry, urinalysis, and reported AEs.

Change from baseline (Visit 4) to each post-treatment time point where scheduled assessments were made will be calculated for relevant measurements. AEs will be summarized by means of descriptive statistics and qualitative summaries.

8.4.2.2 Other significant adverse events

During the evaluation of the AE data, an AstraZeneca medically qualified expert will review the list of AEs that were not reported as SAEs and discontinuations due to AEs.

Based on the expert's judgment, significant AEs of particular clinical importance may, after consultation with the Global Patient Safety Physician, be considered other significant AEs (OAEs) and reported as such in the CSR.

Examples of these are marked haematological and other laboratory abnormalities, and certain events that lead to intervention (other than those already classified as serious), dose reduction, or significant additional treatment.

8.4.3 Calculation or derivation of patient reported outcome variables

SGRQ

Potential health status treatment benefits of benralizumab will be evaluated by comparing the change from baseline at Week 56 in SGRQ Total scores. For the responder analysis of SGRQ

a responder will be defined as an individual with a ≥ 4 -point decrease (improvement) in SGRQ total score at Week 56.

E-RS

Respiratory symptoms will be evaluated using the E-RS. Individual daily E-RS total and subscale scores will be calculated and summarized as a biweekly (14 day) mean. Data collected in the two-week period prior to randomisation will be used to calculate the individual E-RS total and subscale baseline means.

EXACT-PRO

The number, average duration, and severity of EXACT-PRO defined events will be evaluated. EXACT-PRO daily total scores as well as domain scores will be calculated according to the developer approved scoring algorithm. The total score will be used to identify event onset and recovery as well as the magnitude (severity) of the event. The baseline total score will be the mean within subject score over the 7 days prior to randomisation. A minimum of 4 days of data is required for calculating the baseline total score. To allow for improvement or deterioration in disease state over the course of the trial, the baseline total score should be reset every 4 weeks in the absence of an EXACT-PRO defined event. Event frequency is calculated by comparing the baseline with daily total scores. Calculating event duration requires identification of the following five parameters: 1) onset; 2) three-day rolling average; 3) maximum observed value; 4) threshold for improvement; and 5) recovery. The severity of an event is indicated by the worst (highest) EXACT-PRO total score during an event. Complete details concerning variable calculation are provided in the scoring manual and will be provided in the study Statistical analysis plan (SAP).

BDI/TDI

The instrument consists of three components: functional impairment, magnitude of task, and magnitude of effort. For the BDI, each of these three components are rated in five grades from 0 (severe) to 4 (unimpaired), and are summed to form a baseline total score from 0 to 12. The BDI will be captured at baseline only. For the TDI, changes in dyspnea are rated for each component by seven grades from -3 (major deterioration) to +3 (major improvement), and are added to form a total TDI score from -9 to +9.

8.4.4 Calculation or derivation of pharmacokinetic variables

Due to the limited sampling schedule, the PK assessment will be primarily based on the observed steady-state serum trough (predose) concentrations, C_{trough} . Empirical evaluation of potential impact of demographic covariates and ADA on C_{trough} will be conducted.

The PK data will be merged with those from other clinical studies for a population-based meta-analysis. Results of the meta-analysis will be presented in a separate pharmacometrics report outside of the CSR.

8.4.5 Calculation or derivation of immunogenicity variables

ADA assessments will be conducted utilizing a tiered approach (screen, confirm, titer). The presence of anti-benralizumab antibodies is determined relative to a cutoff value that is calculated for each plate as the mean response of the negative control wells multiplied by a cut point factor. The cut point factor was statistically determined during assay validation. Samples that measure at or above the cut point value are considered as potential positives for ADA and are retested in a confirmatory (specificity) assay, both in the absence and presence of excess benralizumab. Samples are confirmed to be positive for ADA if the percent inhibition of response in the presence of benralizumab is greater than or equal to the confirmatory cut point established during assay validation. Confirmed positive samples are then measured in a titer assay. Titers are performed by serially diluting samples with negative control serum and are reported as the reciprocal of the highest dilution (over the 1:50 minimum required sample dilution) that measure positive in the assay, before returning a negative response.

Neutralizing antibody (nAb) evaluations will be conducted on those serum samples that test positive for ADA at end of treatment and also during the study follow up period. ADA-positive samples will be retested in a competitive ligand-binding assay to determine if the ADA present is capable of inhibiting (neutralizing) the binding of benralizumab to soluble recombinant human interleukin 5 receptor (IL-5R). The test sample is deemed positive or negative for the presence of neutralizing antibodies (nAb) to benralizumab relative to a pre-determined (in assay validation), statistically derived cut point. Samples positive for nAb to benralizumab are then titered to determine relative amounts of nAb present in each test sample.

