Assessment/ Activity	Refer to section	R	Treatment												EOT FU	Final FU	Phone FU ^g	UNS ^h			
			V4	V5 phone	V6	V7	V8 phone	V9	V10 phone	V11	V12 phone	V13	V14 phone	V15					V16 phone	V17	V18 phone
		w0	w0	w4	w8	w12	w16	w20	w24	w28	w32	w36	w40	w44	w48	w52	w56				
		d6																			
		+0	+2	+3	+3	+7	+7	+7	+7	+7	+7	+7	+7	+7	+7	+7	+7	+7	N/A	N/A	
Complete physical examination	5.2.1.1	X																X			X
Brief physical examination	5.2.1.2			X	X		X		X		X		X		X						
Weight	5.2.3	X						X										X			
Vital Signs	5.2.4	X		X	X		X		X		X		X		X			X			X
Supplemental O ₂ status	5.3.7	X		X	X		X		X		X		X		X			X			
Oxygen saturation (SpO ₂)	5.3.8	X		X	X		X		X		X		X		X			X			
ECG	5.2.5								X									X			
Pre-BD spirometry	5.1.2	X		X	X		X		X		X		X		X			X			
Clinical chemistry ^b	5.2.6			X	X				X				X					X			
Haematology	5.2.6			X	X				X				X					X			X ^c
Urinalysis	5.2.6			X	X				X				X					X			
Urine pregnancy test (dipstick) ^d	5.2.7	X		X	X		X		X		X		X		X			X			
PK	5.3.4	X		X	X		X		X		X		X		X			X			X

Assessment/ Activity	Refer to section	Treatment																Final FU	Phone FU ^g	UNS ^h			
		R	V4	V5 phone	V6	V7	V8 phone	V9	V10 phone	V11	V12 phone	V13 phone	V14 phone	V15	V16 phone	V17	V18 phone				EOT		
			w0	w0	w4	w8	w12	w16	w20	w24	w28	w32	w36	w40	w44	w48	w52	V19	V20		phone		
			d6															w56	w60				
Visit window (days) ^a																							
		+0	+2	+3	+3	+7	+7	+7	+7	+7	+7	+7	+7	+7	+7	+7	+7	+7	+7	+7	+7	N/A	N/A
ADA/nAb ^e	5.3.5.2	X				X				X		X				X			X				X
Serum for total IgE and IgE FEIA	5.3.3	X								X									X				
Serum/Plasma Biomarkers	5.3.5	X								X									X				
ImmunoCAP ECP	5.3.5.1	X								X									X				
Plasma fibrinogen	5.3.5.1	X								X									X				
Administration of IP ^f	6.8	X								X						X							

^a All visits are to be scheduled from the date of randomisation and not from the date of previous visit. Randomisation visit should occur 21 (± 3) days after Visit 2. If there is a need to postpone Randomisation visit, screening/run-in period can be extended by another 7 days as described in section 4.1.2.

^b Detailed schedule for clinical chemistry tests is provided in section 5.2.6.

^c Eosinophil count to be measured only

^d For WOCBP only, urine HCG test to be done at centre at each treatment visit before the IP administration.

^e nAb will be assessed on all ADA positive samples. Samples that are ADA negative will not be tested for nAb.

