5.3.5.2 Immunogenicity

Instructions for immunogenicity (ADA and nAb) sample collection, processing, storage, and shipment can be found in a separate laboratory manual provided to the centers.

The immunogenicity samples will be retained at AstraZeneca or designee for a maximum of 15 years following the Last Patient's Last Visit.

The analysis time points will be determined by the cumulative information obtained from the Asthma and COPD programs and will be described in SAP.

Summary of the analysis will be presented in the CSR.

Anti-benralizumab antibodies

The pre-dose serum samples to measure presence of ADA will be collected according to the schedule of study procedures (see [Table 3](#)).

The presence or absence of ADA will be determined in the serum samples using validated bioanalytical method. The method will be summarized in the CSR and fully described in the validation report.

Neutralizing antibodies (nAb)

Neutralizing antibodies (nAb) will be assessed on all ADA positive samples. ADA negative samples will not be tested for nAb.

The presence or absence of neutralizing ADA will be determined using a validated bioanalytical method. The method details will be described in a separate bioanalytical report.

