8.5.2.4 Analysis Method for Immunogenicity Variables

Anti-drug antibodies (ADA) to benralizumab will be summarized using descriptive statistics at each visit by treatment group. ADA titers-time profiles of benralizumab by treatment group

will be generated. The impact of ADA on PK and eosinophil level will be assessed. The potential association of ADA with safety and efficacy will be evaluated. The association of the nAb titer with the ADA titer, benralizumab concentration, blood eosinophil levels, and asthma exacerbation rate will be evaluated for ADA positive subjects only.

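### Section 8.4.5 limits neutralising-antibody testing to end of treatment and follow-up, against the all-ADA-positive rule in 5.3.5.2 and Table 3, and 8.5.2.4 names an asthma outcome in a COPD trial

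*Protocol*

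**What the plan says.** Protocol section 5.3.5.2 (Immunogenicity) sets the testing rule without limiting it to any visit: "Neutralizing antibodies (nAb) will be assessed on all ADA positive samples. ADA negative samples will not be tested for nAb". The footnote to the ADA/nAb row of Table 3 repeats it: "nAb will be assessed on all ADA positive samples. Samples that are ADA negative will not be tested for nAb". On sampling, 5.3.5.2 adds: "The pre-dose serum samples to measure presence of ADA will be collected according to the schedule of study procedures". On the form of the result it says: "The presence or absence of neutralizing ADA will be determined using a validated bioanalytical method".

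Section 8.4.5 (immunogenicity variables) states a narrower rule. There, nAb evaluation is for serum samples that "test positive for ADA at end of treatment and also during the study follow up period". It classes each sample as positive or negative against a cut point, and then says: "Samples positive for nAb to benralizumab are then titered to determine relative amounts of nAb present in each test sample".

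Section 8.5.2.4 relates nAb titre to four variables: ADA titre, benralizumab concentration, blood eosinophil level and an exacerbation rate. The sentence ends: "asthma exacerbation rate will be evaluated for ADA positive subjects only".

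**The concern.** The assessment sections and the statistical sections do not describe the same data set. A laboratory working from 5.3.5.2 would test every ADA-positive sample. A programmer working from 8.4.5 would derive nAb variables only from the end of the trial. Immunogenicity is a named secondary objective, and section 1.3 lists reduced efficacy and hypersensitivity as theoretical risks of ADA, so the timing of nAb matters for interpretation. An antibody that neutralises drug during treatment and has gone by week 56 is visible under one rule and invisible under the other.

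The outcome named in 8.5.2.4 is a separate slip in the same analysis. Exclusion criterion 31 rules out asthma as a primary or main diagnosis, and section 8.4.1.1 makes the annual COPD exacerbation rate the primary variable. No asthma exacerbation is defined or scheduled for collection.

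**Working it through.** The protocol states no figure on this point, so the check is a comparison of current text.

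**Which samples are tested**
- 5.3.5.2: all ADA-positive samples.
- Table 3 footnote: all ADA-positive samples.
- 8.4.5: ADA-positive samples at end of treatment and in follow-up. Section 4.3 places the follow-up visit at week 60.

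Two places agree and the third differs. The difference has consequences only if ADA is sampled before end of treatment, and it is: 5.3.5.2 calls for pre-dose samples on the Table 3 schedule. The ADA/nAb row keeps seven marks in the extracted text. The columns from EOT onward are EOT, final follow-up, phone follow-up and unscheduled, so at most 4 marks can sit there. That leaves at least 7 − 4 = 3 marks at earlier visits, one of which may be the pre-dose baseline sample. Column positions are unreliable in the extraction, so this is an approximate lower bound.

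**Who is affected under 8.4.5**
- Any subject whose ADA-positive sample precedes EOT: that sample gets no nAb result, so nAb that appear and resolve go unseen.
- Subjects who stop investigational product early: sections 3.6, 3.6.1 and 4.2.1 bring them back for EOT procedures 12 weeks after the last dose, so they do have an end-of-treatment sample point.
- Subjects who never attend an EOT visit, for example after withdrawal of consent, loss to follow-up or death: under 8.4.5 they have no end-of-treatment sample to test, whatever their earlier ADA results.

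**Which outcome is named**
Of the four variables in 8.5.2.4, ADA titre, drug concentration and eosinophil level are all collected. The fourth, as named, is not. One of four is wrong.

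**Form of the nAb result**
5.3.5.2 speaks of presence or absence. 8.4.5 also classes samples as positive or negative and then titres the positives. The two can coexist, because 5.3.5.2 does not rule out titration. The only statement that titre is not run is the reason given in Amendment 3 for changing the Table 3 footnote and 5.3.5.2. The amendment text shown lists no change to 8.4.5 or 8.5.2.4.

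**The case against.** The best counter-argument is that 5.3.5.2 leaves the immunogenicity analysis time points to the SAP, which is not at hand and may settle the matter. That is fair as regards which time points are summarised. It does not reconcile two fixed and different rules about which samples are tested, both of which stand in the protocol.

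A second objection is that the amendment log describes superseded text, so a mismatch with it is no error. The point does not rest on the log: sections 5.3.5.2, 8.4.5, 8.5.2.4 and the Table 3 footnote are all current. The log is used only to explain why the titre question needs an answer.

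A third is that asthma is an obvious slip for COPD. It probably is, but it still has to be corrected.

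Three stronger readings are tempting and should not be drawn:
- **All early leavers are lost.** A reader might infer that everyone who stops treatment early drops out of nAb testing. The scheduled EOT visit for those who discontinue product contradicts this.
- **The association analysis cannot be run.** Only one of its four variables is misnamed.
- **The titre analysis is contradicted by current text.** It is not: a positive/negative result and a titre of the positives are compatible as written.

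Nor is the information necessarily lost for good, since 5.3.5.2 retains immunogenicity samples for up to 15 years.

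**Conclusion.** Two inconsistencies stand. Section 8.4.5 conflicts with 5.3.5.2 and Table 3 on which samples are tested for nAb, and 8.5.2.4 names an exacerbation outcome that the trial does not define or collect. If 8.4.5 were followed, ADA-positive samples from at least three scheduled marks in Table 3 (possibly including baseline) would carry no nAb result. That count assumes the extracted row has kept all its marks and no spurious ones. How many subjects this would touch cannot be stated, because the protocol gives no expected number of ADA-positive subjects.

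Whether nAb titre exists as a variable is an open question for the sponsor, not a demonstrated contradiction.

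The effect is confined to the secondary immunogenicity analysis. The primary analysis, sample size and type I error are untouched, so this is a minor correction worth making.

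**What to change.** - In 8.4.5, state that nAb is evaluated on all ADA-positive samples, as in 5.3.5.2 and the Table 3 footnote.
- In 8.5.2.4, replace the asthma exacerbation rate with the annual COPD exacerbation rate.
- Confirm with the bioanalytical group whether nAb titre is run. If it is not, drop titration from 8.4.5 and use nAb status (positive/negative) in both 8.4.5 and 8.5.2.4. If it is, say so in 5.3.5.2.

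The cost is wording only. Testing all ADA-positive samples is already planned in 5.3.5.2, so no sampling or assay is added.

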8.5 Methods for statistical analyses

The primary analysis of the primary and key secondary endpoints will include all data captured during the 56-week treatment period, regardless of whether study treatment was prematurely discontinued, or delayed, and/or irrespective of protocol adherence.

Demography and baseline characteristics will be summarized by treatment group for the full analysis set. In the event that there are major differences between the full analysis set and safety analysis set, these summaries will also be repeated for the safety analysis set.

Testing strategy to account for multiplicity considerations

To account for multiplicity to test the primary (exacerbation) and two key secondary endpoints (FEV₁ and SGRQ) for each of the 30mg and 100mg dose groups (for subjects with baseline blood eosinophils $\geq 220/\mu\text{L}$) a testing strategy will be followed to control the overall type I error rate at level 0.05. The testing strategy will be according to the following gate keeping procedure:

Step 1: Perform the two tests of annual COPD exacerbation rate (one test for each dose vs. placebo) at the family wise error rate (FWER) of 0.04 using a Hochberg Procedure ([Hochberg](#))

[figure not shown]
1988). If both p-values are less than 0.04, then proceed to Step 2; else if the smaller p-value is less than 0.02 then proceed to Step 2a; otherwise no null hypothesis is rejected

Step 2: Test the two key secondary endpoints for both doses as one family at the FWER of 0.05 using a Holm Procedure (Holm 1979).

Step 2a: Test the two secondary endpoints for the smaller-p-value dose at the FWER of 0.01 using a Holm Procedure.

The gatekeeping procedure is also shown in the diagram below:

Figure 4 Gatekeeping Procedure

Since the correlation of the two test statistics for COPD exacerbation rate in the Step 1 is positive, the FWER of the Hochberg Procedure is strongly controlled at 0.04. The overall FWER of the gatekeeping procedure is strongly controlled at 0.05.

For the comparison of the 10mg dose group and placebo in subjects with baseline blood eosinophils $\geq 300/\mu\text{L}$, multiplicity will be adjusted for the testing of the primary and two key secondary endpoints using a serial gatekeeping procedure (Dmitrienko and Tamhane 2007). In the procedure the primary endpoint will be tested at 0.05 level for the comparison of the 10mg dose group and placebo. The two secondary endpoints will be tested using a Holm procedure at the 0.05 level for the comparison of the 10mg dose group and placebo only if the test for the primary endpoint is significant at 0.05 level.

In summary the FWER will be strongly controlled for the comparison of 30mg and 100mg vs. placebo at 0.05 on testing of the primary endpoint and two key secondary endpoints. The FWER will also be strongly controlled for the comparison of 10mg vs. placebo at 0.05 on

testing of the primary endpoint and two key secondary endpoints. The FWER will not be strongly controlled at 0.05 for the testing of the primary endpoint and two key secondary endpoints across all three doses.

